1.2.2 SMART Secondary Aims

There are 3 secondary aims. The first secondary aim is to compare the effect of tapering with termination at the 2nd randomization among those who received CPS as well as those who received SMS and achieved early response (SRA originally was VL <200). This will be done again first by a comparison of two SRA rates among the two groups (tapering vs. termination), followed by more refined analysis using LME modeling. The second secondary aim is to compare the effect of CPS and SMS tapering vs. termination among the responders. We will first perform a χ^2 test between the two viral suppression rates, followed by mixed-effects modeling. The purpose of the second, secondary aim is to determine which of the eight adaptive interventions embedded within the SMART (listed in **Section A.5** in original proposal) leads to the greatest improvement in VL and SRA over the entire study period (48 weeks). To perform this, we will estimate the viral suppression rates and adherence rates among the subjects following each of the eight embedded adaptive interventions, and conduct a χ^2 test. Since in the current study, both responders and non-responders are re-randomized, there is no need to use inverse-probability weighting¹⁰⁶ of the study sample. However, in order to account for the correlation induced by subjects shared between any two embedded adaptive interventions, we will use *robust (sandwich) standard errors* as in the *generalized estimating equations* approach.¹⁰⁷ The final secondary aim is to study the moderators of treatment effect. This is a very interesting goal, given the gradual but assured paradigm shift in behavioral interventions from “one-size-fits-all” approach to the modern personalized medicine. Potential moderators in the current context are subject’s demographics and the level of motivation – these can be incorporated in the analysis of the SMART data to deeply personalize the adaptive intervention for future patients. Because of the two-stage nature of the adaptive interventions, unfortunately a straightforward regression analysis including potential moderators in the model as interaction terms is not suitable due to the possibility of ‘collider-stratification bias’ – a type of selection bias that can be present in time-varying settings, even in presence of randomization, e.g. in a SMART.¹⁰⁸ To avoid this kind of bias, one needs to employ 2 separate regressions corresponding to the 2 stages of SMART, and carefully move backward through the stages; such a state-of-the-art approach is known as Q-learning.¹⁰⁹ Each of these regressions will contain interaction terms between the stage-specific treatments and the appropriate stage-specific moderators. If any of these interactions come out significant, then the corresponding patient characteristics can be used to deeply tailor the interventions for future patients. This analysis will be performed using the R software package *qLearn* (<http://cran.rproject.org/web/packages/qLearn/index.html>). Secondary aims are not powered.

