We will also conduct similar models as above however predicting adherence to ART (secondary outcome), which is measured at every time point. Each model will be a two-level model in which time points (Level 1) are nested within participants (Level 2). This approach accounts for the non-independence of repeated measurements within individuals. The purpose of the LME based [64] analysis for the primary aim is to determine which of the first-stage intervention, CPS or SMS, is associated with the most improvement in VL and adherence, regardless of which second-stage treatment participants received. Also note in SMART design, we compare combinations of subgroups (as in two Specific aims), but not individual subgroups. The study is designed and powered to test the two primary hypotheses with one primary outcome. However, we expect that data based on SMART design will yield valuable information for hypotheses generation involving high quality embedded interventions, which can guide the design of subsequent confirmatory studies.

SMART Secondary Aims. The first of the secondary aims is to compare the effect of tapering with termination at the second randomization among those who received CPS and those who received SMS and achieved VL <200 copies/mL. The AC will compare viral suppression rates among the two groups (tapering vs. termination), followed by more refined analysis using LME modeling. We will first perform a χ^2 test between the two viral suppression rates, followed by mixed-effects modeling.

The purpose of the second secondary aim is to determine which of the adaptive intervention arm leads to the greatest improvement in VL and adherence over the entire study period. To perform this, we will estimate the viral suppression and adherence rates following each of the 8 embedded interventions, and conduct a χ^2 test. Since both responders and non-responders are re-randomized, there is no need to use inverse-probability weighting [65]. However, in order to account for the correlation induced by subjects shared between any two embedded interventions, we will use robust (sandwich) standard errors as in the generalized estimating equations approach [66].

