1.1 Data Management and Data Quality

The first randomization involves allocation to CPS vs. SMS using a 1:1 allocation ratio. This step will use stratified randomization in permuted blocks to achieve balance in distribution of behaviorally and perinatally infected youth. The REC data team will program the randomizer in Qualtrics and will not participate either in the intervention delivery or in the adherence reinforcement steps. The protocol team will monitor race, ethnicity, and gender to ensure balanced distribution at the first stage. After 6 months, stratified randomization will occur with permuted blocks within each trajectory. Since second stage randomization is dependent on first stage response status, we will only maintain the balance within each first stage treatment outcome when randomizing at the second stage.

Following the Analytic Core's (AC) standard quality assurance, including checking for outliers and abnormal values using graphical methods, we will verify that the distributions of measures meet the assumptions of the statistical tests to be used, applying a formal test such as the Shapiro-Wilk's test [60]. Transformations will be used when distributional assumptions are not fulfilled. Tests will be conducted to identify potential relationships among baseline demographic and clinical variables and our dependent variables and to see whether they are balanced between groups. If a baseline variable is not balanced between groups and is correlated with the dependent variable ($r > .30$), we will include this variable as a covariate in subsequent analyses. Since we will test more than one primary hypothesis with one primary outcome variable (VL suppression), the Hochberg step-up multiplicity adjustment will be used with a two-tailed family wise alpha-level of .05 [61]. All other tests described below will each have a two-tailed alpha-level of 0.05. Outcome analyses will be based on the principle of intention-to-treat [62].

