1.2.4 Sample Size and Power

Sample Size and Power. Statistical power analyses examined the sample size requirements to detect greater than chance group differences on primary outcome (PH1 and Ph2). We have used Susan's formula with a total sample size of 120.

<http://people.seas.harvard.edu/~samurphy/papers/APPProof.pdf>

| Power Table | | | |
|--------------------|------------|------------|-----------------------------|
| ES | p | N | N(10% attrition adjustment) |
| 0.55 | 0.4 | 86 | 96 |
| | 0.5 | 104 | 116 |
| | 0.6 | 130 | 144 |
| | 0.7 | 174 | 192 |
| 0.6 | 0.4 | 74 | 80 |
| | 0.5 | 88 | 98 |
| | 0.6 | 110 | 120 |
| | 0.7 | 146 | 160 |

Alternatively, for the two groups comparison this corresponds to n=60/group. This sample size is sufficient to provide 80% power (or more) for a standardized Effect Size (ES) of 0.55 or more, using a t-distribution for a two tailed test with $\alpha=0.05$, with 10% attrition assuming equal responder rate (p) in both arms.

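### The plan sets out to identify the best of eight overlapping sequences, but one chi-square test cannot do that; a raw ranking would flatter the winner by about 9 to 12 points if no sequence truly differs

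*SAP*

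**What the plan says.** SAP 1.2.2 gives the purpose of this secondary aim as a determination: it "is to determine which of the eight adaptive interventions embedded within the SMART" is the one that "leads to the greatest improvement in VL and SRA over the entire study period (48 weeks"). Protocol 16.0 (SMART Secondary Aims) likewise sets out to "determine which of the adaptive intervention arm leads to the greatest improvement in VL and adherence over the entire study period".

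The method is to estimate the rates among participants "following each of the eight embedded adaptive interventions, and conduct a χ^2 test". Robust standard errors are added "in order to account for the correlation induced by subjects shared between any two embedded adaptive interventions". SAP 1.1 sets the level for tests outside the primary hypotheses: "All other tests described below will each have a two-tailed alpha-level of 0.05".

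Neither document gives a rule for moving from eight rates to one choice, an interval for the chosen sequence, or a rule for the case where VL and SRA favour different sequences.

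Other places limit the aim. SAP 1.2.2 says the secondary aims are not powered. Protocol 16.0 adds that they are exploratory. Protocol 1.0 and SAP 1.2 both use *explore* for this comparison. In SAP 1.2 the list of original secondary aims ends with a bracketed note that something was not completed because of low retention. The note follows item (c), and the sequence comparison is item (b), so it is unclear whether the note covers it.

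**The concern.** A chi-square test across eight rates addresses equality. If it rejects, it does not say which sequence is best; if it does not reject, it gives no ground for naming one. Under this plan the only route to a best sequence is to take the largest of eight estimates, each resting on about a quarter of the sample.

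The largest of several noisy estimates overstates the truth on average. Robust standard errors make the variances right when people count towards more than one sequence, but they do not correct for having picked the maximum. A second outcome allows a second winner.

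At stake is what is carried forward. Protocol 16.0 (Quantitative Analysis Plan) expects the embedded-intervention data to guide the design of later confirmatory studies. A sequence chosen largely by chance, with an inflated rate, is a poor basis for choosing and sizing the next trial.

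**Working it through.** **The plan's own figure.** The documents give no figure for the eight-sequence comparison. The power statement in SAP 1.2.4 concerns two groups. Its entry for effect size 0.55 and responder rate 0.5 reproduces: 2(1.960 + 0.842)² / (0.55² × 0.5) = 103.8, so 104, and 104/0.9 = 115.6, so 116. It says nothing about ranking eight sequences.

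**Inputs**
- Sample: "total sample size of 120" (SAP 1.2.4).
- First stage: 1:1 (SAP 1.1), so 60 per arm.
- Second stage: two options for responders and two for non-responders in each arm (Protocol 5.0, Randomization Process/Systems). The ratio is not stated; equal splits are assumed.
- Responders after stage 1: about 50% (Protocol 16.0, Sample Size and Power).
- Attrition: 10% (SAP 1.2.4).
- Final rate per sequence: not given. Assumed 0.50, varied from 0.2 to 0.8. The only suppression rate in the documents is the 27% background figure in Protocol 2.0.

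**Step 1, size of a sequence.** There are 2 × 2 × 2 = 8 sequences. Each arm has 30 responders and 30 non-responders, each split 15/15. A sequence uses one responder cell and one non-responder cell: 15 + 15 = 30 people, or 27 after 10% attrition.

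**Step 2, standard error.** At a rate of 0.50, √(0.25/30) = 0.0913, or 9.1 points.

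**Step 3, expected maximum with the overlap kept.** In standard-error units a sequence estimate is (X_R + X_N)/√2, where X_R and X_N are independent standardised cell means.
- The best of two cells averages 1/√π = 0.564.
- The best sequence within an arm averages 2 × 0.564/√2 = 0.798, with standard deviation √(1 − 1/π) = 0.826.
- The better of two arms adds about 0.826 × 0.564 = 0.466.
- Total: about 1.264. Simulation of the same structure gives 1.263.

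The upward bias is therefore 1.263 × 9.13 = 11.5 points, and by symmetry the best-worst gap is about 2 × 11.5 = 23 points. Treating the eight sequences as independent would overstate the bias at about 13 points.

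**Step 4, simulation with binary outcomes and no true difference between sequences**

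| Assumption | Mean excess of the top-ranked rate |
|---|---|
| Rate 0.50, about 30 per sequence | 11.5 points (gap 23) |
| Rate 0.27 | 10.4 |
| Rate 0.20 | 9.4 |
| Rate 0.80 | 8.8 |
| Responders 80%, non-responders 20% | 9.8 |
| Rate 0.50, 10% attrition | 12.1 |
| Rate 0.50, 30% attrition | 13.7 |

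At a rate of 0.50, a responder fraction of 30% instead of 50% changes the result little (about 11.4 points).

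**Step 5, if sequences truly differ.** The bias is measured against the true rate of the sequence actually chosen.
- Both pairs of second-stage options differ by 10 points, arms equal: 10.3 points. One of the two truly best sequences is chosen 54% of the time.
- Both pairs differ by 20 points: 7.9 points with equal arms, 6.6 if the arms differ by 10 points, 4.6 if they differ by 20.

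**The case against.** The strongest reply is that the documents already hedge this aim. It is unpowered, exploratory, described as *explore* in the formal list of aims, and meant to generate hypotheses, with confirmation left to a separate study. If the low-retention note covers it, no winner will be named. The SAP also does not say that the top rate will be reported as unbiased or without an interval. Much of this stands: it confines the point to interpretation and planning. It does not close the gap, because SAP 1.2.2 and Protocol 16.0 still state a determination and still offer a test that cannot deliver one. Lack of power is also what makes the leading estimate so inflated.

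A reader might go further and infer that all 28 pairs (8 × 7/2) will be tested at 0.05, from the wording "correlation induced by subjects shared between any two embedded adaptive interventions" together with the general 0.05 rule. With no true difference, such testing would give at least one false positive in about 41% to 43% of trials. The documents do not support that reading. They state one chi-square test and no pairwise tests; the wording describes the correlation that the robust covariance handles, which a valid omnibus test needs in any case. A robust omnibus test on 5 degrees of freedom, the nearest reading of the plan, rejects in about 8% to 9% of such trials, and so would pairwise tests read only after it. The 41% to 43% also assumes equal final rates in responders and non-responders. At 80% and 20% it falls to about 24% without the omnibus gate and about 2% with it.

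A second tempting reading is that the winner will be 11 points too good whatever the truth. That figure belongs to the case of no true difference.

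**Conclusion.** The point holds as a mismatch between aim and method. The stated test cannot identify a best sequence, and nothing in the plan links eight rates and two outcomes to one choice.

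If the raw ranking is used and no sequence truly differs, the top rate is overstated by about 11 points at a rate of 0.50, and by about 9 to 12 points over rates of 0.2 to 0.8 and the planned 10% attrition. The best-worst gap averages about 23 points by chance at a rate of 0.50. If both second-stage choices truly matter by 20 points, the overstatement is about 5 to 8 points. These figures rest on equal second-stage splits, about 50% responders and assumed final rates, because the documents give neither the splits nor the rates.

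The primary result is not affected. This is a low-cost improvement to an exploratory aim, and it falls away if the aim has been dropped.

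**What to change.** First state in SAP 1.2.2 whether the sequence comparison is still to be analysed, so that it agrees with the low-retention note in SAP 1.2. If it is kept:

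1. Supplement or replace the omnibus chi-square with multiple comparisons with the best, using the same eight estimates and the same robust covariance matrix. Report the set of sequences that cannot be excluded as best at simultaneous 95% confidence.
2. Name one outcome, VL suppression or SRA, for the ranking, and show the other as supportive.
3. Change *determine* to *explore* in SAP 1.2.2 and in Protocol 16.0, in line with SAP 1.2 and with the exploratory label in Protocol 16.0.

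The cost is a few lines of SAP and protocol wording and a little extra programming, with no new data. The downside is that at this size most or all eight sequences may remain in the set. That would be a fair account of what about 30 people per sequence can show.

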
1.2.3 Site Clustering Effects

Although some of the participants will be recruited via a site referral, we do not anticipate substantial site effects. A group identifier for each participant will be included in the merged analytic dataset, and the intra-class correlation (ICC) for each outcome within sites will be calculated prior to conducting multivariate analysis. If no significant variance (<0.05) is carried at the group level, we will reduce the

model to a traditional two-level model (only clustering due to repeated measure). If significant group-level variance does emerge, dummy codes to control for site-specific variance will be used to enhance statistical power using a 3-level LME model. In other words, ICC will be included in the model at three-level to control for the clustering effect by design, provided third level is significant. The significance test is always at 0.05. We did not recommend a three-level model all the time as power analysis is conducted considering two-level models only i.e. ignoring site effect.

1.2.4 Sample Size and Power

Sample Size and Power. Statistical power analyses examined the sample size requirements to detect greater than chance group differences on primary outcome (PH1 and Ph2). We have used Susan's formula with a total sample size of 120.

<http://people.seas.harvard.edu/~samurphy/papers/APPProof.pdf>

| Power Table | | | |
|--------------------|------------|------------|-----------------------------|
| ES | p | N | N(10% attrition adjustment) |
| 0.55 | 0.4 | 86 | 96 |
| | 0.5 | 104 | 116 |
| | 0.6 | 130 | 144 |
| | 0.7 | 174 | 192 |
| 0.6 | 0.4 | 74 | 80 |
| | 0.5 | 88 | 98 |
| | 0.6 | 110 | 120 |
| | 0.7 | 146 | 160 |

Alternatively, for the two groups comparison this corresponds to n=60/group. This sample size is sufficient to provide 80% power (or more) for a standardized Effect Size (ES) of 0.55 or more, using a t-distribution for a two tailed test with $\alpha=0.05$, with 10% attrition assuming equal responder rate (p) in both arms.

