1.2 Quantitative Analysis Plan

Original Primary Hypotheses: 1. Youth randomized to CPS will have significantly greater VL suppression (primary outcome) and self-reported medication adherence (secondary outcome) at 24 weeks than those in SMS group. 2. Non-responders randomized to CPS with incentives will have significantly greater VL suppression (primary outcome) and self-reported adherence (secondary outcome) than those randomized to SMS with incentives.

Original Secondary Aims: a) Conduct an exploratory evaluation of tapering the intensity of CPS and SMS (among responders) vs termination after completion of the 24 week intervention to determine if this improves the durability of intervention effects; b) Explore the relative efficacy of the individual intervention sequences embedded within the SMART design for responders and non-responders; and c) Describe moderators of the treatment effect, including demographics, mode of infection, substance use, and mental health. [NOT COMPLETED DUE LOW RENTENTION]

Updated Primary Outcome: Originally, we plan to treat VL suppression as our primary outcome for both co-primary hypothesis. Primary end-point for H1 was at 24 weeks when the proximal outcome was used to determine responder status, while for H2 the Distal outcome was at end of 12 months (or 72 weeks). Due to the difficulty in collecting viral load we proposed to change the primary outcome to a combination of VL suppression and self-reported adherence (SRA). Primary end-points for both co-primary hypothesis is now at 48 week.

Rationale of new definition of Primary Outcome: Since the VLS data may not be available for a significant number of subjects, we plan to use SRA as an additional primary outcome. The usefulness and appropriateness of the usage of these two depends upon the concordance of two measures. To determine that for those subjects we have both VLS and SRA data available, we will first construct a 2×2 contingency table and conduct a chi-square test of association. If they agree on 80% or more cases we will proceed to define (and analyze) the primary outcome as following:

- 1) For any data collection point and randomization event, if VLS data is available it will be used as primary outcome. When VLS data is not available, SRA will be used as primary outcome. This composite definition will be used as primary outcome and will have sufficient power based on hypothesized effect size.

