1.2.1 Primary Analysis Plan

The primary analysis will be a comparison of SRA (primary outcome) between the CPS and the SMS group at the end of first stage of randomization. This will be performed using a χ^2 test. We will also compare the VL suppression between the two groups for those available subjects, albeit this is no longer treated as primary outcome. Since SRA (and VL) is a continuous measure, we will use two-sample t-test to conduct this analysis. We will also compare the self-reported medication adherence rate (secondary outcome) between the two groups using a χ^2 test. All the primary analyses will be based on initial assignment to groups, using the ITT principle. Each of the primary hypotheses will be tested using linear mixed-effects (LME) regression analyses.¹⁰⁴ For testing primary hypothesis 1 (PH1), the model will include up to 3 repeated assessments of VL suppression (weeks 0/baseline, 12, 24, 36, 48). For primary hypothesis 2 (PH2), we will only focus on non-responders (for both CPS and SMS at stage 1) and compare the SRA as dependent variable using a repeated measure LME (weeks 0/baseline, 12, 24, 36, 48). In an effort to get the outcome for PH2 some subject may have final outcome at latter date than 48 weeks. Each LME model will include a random intercept and slope and fixed effects for adherence intervention group, and time, as well as the stratification variables: clinical site, age, gender. A likelihood ratio test will examine the incremental contribution of the group by time interaction, which represents the interaction of interest for PH1 and PH2, testing for a differential adherence intervention effect over time. The decision rule for each primary hypothesis calls for rejection of H_0 if this interaction is statistically significant using the Hochberg adjustment. A site by group interaction will be also examined and included in each model (above) if significant at the 0.05 level. The purpose of the LME based analysis for the primary aim is to determine which of the first-stage intervention, CPS or SMS, is associated with the most improvement in VL and adherence, regardless of which second-stage treatment participants received. Due to contraction of sample size compared to our original plan, we do not plan to adjust α for multiple of testing. In addition to PH1, for those subjects we have VL suppression data available we would perform similar LME to test for its significance. We also expect some subjects with complete VL data and many with partial VL data for

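### SAP 1.2.4 offers one power analysis for both co-primary hypotheses at 120 participants, but PH2 has about 51% power at ES 0.55 with 50% responders, not 80%

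*SAP*

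**What the plan says.** SAP 1.2.4 states that its power analyses "examined the sample size requirements to detect greater than chance group differences on primary outcome (PH1 and Ph2"), "with a total sample size of 120". A table follows with N, before and after a 10% attrition adjustment, for ES 0.55 and 0.60 and responder rates p from 0.4 to 0.7. The table names no hypothesis and does not say whether N is a total.

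The text then recasts the total as 60 per group when two groups are compared, and makes this claim: "This sample size is sufficient to provide 80% power (or more) for a standardized Effect Size (ES) of 0.55 or more", by a two-tailed t-test at alpha 0.05, "with 10% attrition assuming equal responder rate (p) in both arms".

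PH2 is defined in SAP 1.2: "Non-responders randomized to CPS with incentives will have significantly greater VL suppression (primary outcome") than those given SMS with incentives. For its analysis, SAP 1.2.1 says "we will only focus on non-responders (for both CPS and SMS at stage 1"). Protocol 5.0 (Randomization Process/Systems) randomizes those non-responders between the two incentive arms and gives no allocation ratio. Protocol 16.0 describes the study as powered for both primary hypotheses. Its own calculation, however, is for 190 participants, with about half responding at stage 1. No other power figure for PH2 at 120 appears in either document.

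**The concern.** PH2 uses only part of the sample, and that part is divided between two arms. A total that just gives PH1 80% power at ES 0.55 cannot give PH2 the same power at the same effect size unless almost nobody responds at stage 1. The section nevertheless introduces one analysis for both hypotheses and gives PH2 no figure of its own.

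The table adds to the problem. At ES 0.55 its attrition-adjusted entries for p = 0.4 and 0.5 are 96 and 116, both below 120. At ES 0.60 the entries for p = 0.4, 0.5 and 0.6 are 80, 98 and 120. A reader would conclude that 120 is enough for PH2 in those five rows. The ES 0.55 rows for p = 0.6 and 0.7 (144 and 192) and the ES 0.60 row for p = 0.7 (160) already exceed 120, so the shortfall there is visible.

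PH2 is one of two co-primary hypotheses. If it is believed to have 80% power when it has about half, a non-significant result may be read as evidence that the two incentive arms do not differ.

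**Working it through.** **Inputs.** From SAP 1.2.4: 120 enrolled, 10% attrition (120 x 0.9 = 108), ES 0.55 and 0.60, p = 0.4 to 0.7, two-sided t-test at alpha 0.05. From Protocol 16.0: p of about 0.5. Assumed: 1:1 second-stage allocation, and equal attrition in responders and non-responders.

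**1. The stated 80%.** PH1 has 60 x 0.9 = 54 per group. The noncentrality is ES x sqrt(n/2) = 0.55 x sqrt(27) = 2.86 on 106 degrees of freedom. Power is 80.8%, so the sentence reproduces for PH1.

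**2. The table.** The normal-approximation number per arm for 80% power is 2 x (1.96 + 0.8416)^2 / ES^2 = 15.70 / ES^2, which is 51.9 at ES 0.55 and 43.6 at ES 0.60. The printed unadjusted N times (1-p) gives:

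| ES | p = 0.4 | p = 0.5 | p = 0.6 | p = 0.7 |
|---|---|---|---|---|
| 0.55 | 86 x 0.6 = 51.6 | 104 x 0.5 = 52.0 | 130 x 0.4 = 52.0 | 174 x 0.3 = 52.2 |
| 0.60 | 74 x 0.6 = 44.4 | 88 x 0.5 = 44.0 | 110 x 0.4 = 44.0 | 146 x 0.3 = 43.8 |

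All eight rows follow N = n per arm / (1-p). Read as a total, N supplies enough non-responders for one arm, but PH2 divides them between two. Splitting each count in half gives t-test power of 49% to 50% in every row. A total for PH2 would need 2n/(1-p): at ES 0.55 and p = 0.5 that is 2 x 52 / 0.5 = 208, not 104.

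**3. PH2 at 120 enrolled.** The number per arm is 108 x (1-p) / 2. At p = 0.5 this is 27, the noncentrality is 0.55 x sqrt(13.5) = 2.02 on 52 degrees of freedom, and power is 50.9%.

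| p | n per arm | Power, ES 0.55, alpha 0.05 | Power, ES 0.60, alpha 0.05 | Power, ES 0.55, alpha 0.025 | ES detectable with 80% power, alpha 0.05 |
|---|---|---|---|---|---|
| 0.4 | 32.4 | 58.7% | 66.2% | 47.1% | 0.71 |
| 0.5 | 27.0 | 50.9% | 58.1% | 39.4% | 0.78 |
| 0.6 | 21.6 | 42.3% | 48.6% | 31.3% | 0.87 |
| 0.7 | 16.2 | 32.9% | 38.0% | 23.0% | 1.02 |

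With no attrition at all, p = 0.5 leaves 30 per arm and 55.4% power at ES 0.55.

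**4. What 80% would take.** The exact t-test needs 53 per arm at ES 0.55. At p = 0.5 that is 2 x 53 / 0.5 = 212 evaluable, or 212 / 0.9 = 235.6, so 236 enrolled. With 108 evaluable, 53 per arm requires 1-p = 106/108, a responder rate of about 2%.

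**5. Alpha.** SAP 1.1 specifies Hochberg, and SAP 1.2.1 rejects each null hypothesis "if this interaction is statistically significant using the Hochberg adjustment", yet SAP 1.2.1 also says alpha will not be adjusted. Hochberg with two hypotheses rejects one if its p-value is at most 0.025, or if both are at most 0.05. Its power therefore lies between the 0.025 and 0.05 values. At ES 0.55 that is 72% to 81% for PH1, and 39% to 51% for PH2 at p = 0.5.

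**The case against.** The strongest reply is that the 80% sentence speaks of a two-group comparison with 60 per group. PH2 cannot have 60 per group, so the sentence must mean PH1, and for PH1 it is right. This is a fair reading and the arithmetic supports it. But the sentence names no hypothesis, ends with a condition on the responder rate that a comparison of all randomized participants does not need, and stands in a section that announces both hypotheses. If it is for PH1 only, PH2 has no power statement.

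Second, what the table was built for is inferred from its 1/(1-p) scaling, because the cited formula is external. N might be meant per first-stage arm, which would make the rows correct for PH2. That uncertainty stands, so the 212/236 correction is conditional on N being a total for PH2. It does not help PH2: on the per-arm reading, ES 0.55 with p = 0.5 needs 208 before attrition, against 120 enrolled. The 51% does not depend on how the table is read.

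Third, the decision rule is a group-by-time interaction in a mixed model, not a t-test. The SAP states its power on a t-test and gives no inputs for the mixed model, so the t-test is the right basis for checking it. A rough check uses the protocol's within-subject correlations of 0.30 to 0.50, a random intercept only, five equally spaced visits and a linear difference reaching 0.55 SD. The standard error is sqrt(2(1-ICC)/(27 x 0.625)), or 0.288 to 0.243, giving about 48% to 62% power at 27 per arm. A random slope, which the plan includes, would lower this. The 51% is therefore not exact for the planned test, but this check stays well below 80%.

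Fourth, the 50% responder rate comes from the 190-participant calculation. Protocol 5.0 counts a missing 3-month viral load as non-response, which would enlarge the PH2 set. SAP 1.2 lets self-reported adherence stand in for missing viral load at randomization, which could also change p. This is a good reason to report the range, but even p = 0.4 gives only 59%.

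**Conclusion.** The concern holds. At 120 enrolled with 10% attrition, a two-sided single-time t-test at alpha 0.05 and ES 0.55, PH1 has 81% power. PH2 has 51% at the protocol's 50% responder rate, and 59% to 33% across the table's range of 0.4 to 0.7. PH2 reaches 80% only for an ES of about 0.78 at p = 0.5 (0.71 to 1.02 over the range). The figures rest on 1:1 second-stage allocation and on equal attrition in responders and non-responders. That the table was intended for PH2 is an inference. This should be fixed, because SAP 1.2.4 and Protocol 16.0 present a co-primary hypothesis as powered when, at these effect sizes, it is not.

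**What to change.** No further enrolment is asked for.

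1. Name PH1 in the 80% sentence of SAP 1.2.4.
2. State which hypothesis N in the table is for and whether it is a total. If it is meant as a total for PH2, replace it with 2n/(1-p), for example 212 before and 236 after attrition at ES 0.55 and p = 0.5.
3. Add a PH2 sentence along these lines: with 120 enrolled, 10% attrition and 1:1 second-stage allocation, power at ES 0.55 is about 51% for a responder rate of 0.5 (59% to 33% for 0.4 to 0.7); 80% power requires an ES of about 0.78 at 0.5, so PH2 is powered only for large effects. If the ES 0.60 rows are kept, give 66%, 58%, 49% and 38% beside them.
4. Say for both hypotheses that the figures assume a single-time t-test at alpha 0.05 and do not quantify the mixed-model interaction test. If Hochberg is retained, add the 0.025 figures at ES 0.55: PH1 72%, PH2 47% to 23%.
5. Bring the 190-participant power statement in Protocol 16.0 into line with 120, at whichever alpha is kept.

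The cost is wording in SAP 1.2.4 and Protocol 16.0 and a table label. Enrolment, endpoints and analyses stay as they are. The price is a less favourable stated power for PH2.
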